# 5.4.1.1.8. Virologic Breakthrough

HBV virological breakthrough is defined as having a confirmed on-treatment HBV DNA increase by  $>1 \log_{10}$  from nadir level (lowest level reached during treatment) in participants who didn't have on-treatment HBV DNA level below the lower limit of quantification (LLOQ) or a confirmed on-treatment HBV DNA level >200 IU/mL in participants who had on-treatment HBV DNA level below the lower limit of quantification (LLOQ). Confirmed HBV DNA increase/level means that the criterion should be fulfilled at 2 or more consecutive time points or at the last observed time points or at the last observed on-treatment time point. On-treatment will be defined as the time period in which the participant receives any of the study interventions (including NA).

In addition, participants who experience a virologic breakthrough followed by on-treatment biochemical flare will be evaluated.

## 5.4.1.1.9. Flares

The criteria based on blood markers/lab tests for each of the flare types are defined below.

**On-treatment Biochemical flare** is defined as follows:

The start date of a confirmed on-treatment biochemical flare is defined as the first date of two consecutive visits with ALT and/or AST $\ge$ 3x ULN and  $\ge$ 3x nadir (i.e. lowest value observed up to the start of the flare) while the participant receives any of the study interventions. The end date of the same on-treatment biochemical flare is defined as the first date when there is a 50% reduction from the peak ALT and/or AST level & <3x ULN, regardless of stopping the study interventions.

- 1 (Yes) = confirmed\*\* ALT and/or AST ≥3x ULN and ≥3x nadir (i.e. lowest value observed up to the start of the flare)
- 0 (No) = otherwise

\*\* Confirmed means that the criterion should be fulfilled at 2 or more consecutive time points or at the last observed time point.

# 5.4.1.2. Continuous Endpoints

# 5.4.1.2.1. HBsAg, HBeAg, HBV DNA and ALT

Actual values (original unit and/or log10 transformed values), changes from baseline (log10 transformed values) and change from RTs over time in HBsAg will be evaluated, and actual values (original unit and/or log10 transformed values), over time in HBeAg, HBV DNA and ALT will be evaluated.

Change from baseline is defined as the value at a given time point minus baseline value.

The change from baseline value to the nadir (i.e. maximum decrease for each participant) in HBsAg will be evaluated at 3 intervals: during study intervention nadir (first 24 weeks), during follow-up nadir, and entire study nadir.

## 5.4.2. Analysis Methods

Summaries and graphs will be provided for each intervention arm and analysis phase, unless specified otherwise.

Statistical comparisons of the secondary endpoints among intervention arms may be done with no adjustment for multiplicity.

All secondary endpoints will be analyzed based on the observed case data. Additional analyses with specific imputation methods for missing data are added for selected endpoints.

Inferential and descriptive subgroup analyses may not be performed if there are not enough data to perform the analyses.

# 5.4.2.1. Binary Endpoints

The count and proportion (%) of participants achieving the endpoints defined in Section 5.4.1.1 will be summarized. The associated 90% CI will be included for the following endpoints:

- HBsAg seroclearance
- HBsAg seroconversion
- Suppressed HBV DNA
- ALT Normalization
- Virologic Breakthrough
- Flares

For all time points, binary endpoints will be analyzed using the observed case data. LOCF (Section 5.4.2.1.1) will be used for HBsAg seroclearance and Suppressed HBV DNA analyses at Week 24, FU Week 12, FU Week 24, FU Week 32 and FU Week 48.

The HBsAg seroclearance analyses at Week 24, FU Week 12, FU Week 24, FU Week 32 and FU Week 48 will be compared between treatment arms using a 2-sided 90% CI of the difference in proportions between the treatment groups (Arm 1 minus Arm 2) that will be constructed using a Mantel-Haenszel test controlling for stratification factor.

For single arm, point and 90% CI estimates, the Clopper Pearson method will be used.

Subsections below describe the additional analyses planned for only those specific other secondary binary endpoints that require further evaluations.

# 5.4.2.1.1. LOCF Imputation Method

- If the lab value at Week 24 is missing, the LOCF approach will be used with the condition that no value earlier than Week 20 may be carried forward.
- If the lab value at FU Week 12 is missing, the LOCF in conjunction with the next available observation imputation approach will be used. The available non-missing lab test closest to

FU Week 12 which is no earlier than FU Week 4 and no later than FU Week 24 will be imputed. If the non-missing lab value before and after the specific timepoint fall equidistant from the target timepoint, the later one will be used to impute the missing value.

- If the lab value at FU Week 24 is missing, the LOCF in conjunction with the next available observation imputation approach will be used. The available non-missing lab test closest to FU Week 24 which is no earlier than FU Week 12 and no later than FU Week 32 will be imputed. If the non-missing lab value before and after the specific timepoint fall equidistant from the target timepoint, the later one will be used to impute the missing value.
- If the lab value at FU Week 32 is missing, the LOCF in conjunction with the next available observation imputation approach will be used. The available non-missing lab test closest to FU Week 32 which is no earlier than FU Week 24 and no later than FU Week 48 will be imputed. If the non-missing lab value before and after the specific timepoint fall equidistant from the target timepoint, the later one will be used to impute the missing value.
- If the lab value at FU Week 48 is missing, the LOCF approach will be used with the condition that no value earlier than FU Week 32 may be carried forward.

# 5.4.2.1.2. HBsAg Seroconversion

For participants achieving HBsAg seroconversion, descriptive statistics will be calculated for the level of anti-HBs antibodies at the timepoint when achieving the HBsAg seroconversion. In an additional summary, the level of anti-HBs antibodies at the specific timepoint will be summarized for the subset of the participants achieving HBsAg seroconversion at any time before or at that given timepoint.

In addition, the count and proportion of participants (and associated 90% CI) with appearance of anti-HBs antibodies but without seroclearance of HBsAg will also be summarized by intervention arm and analysis phase.

# 5.4.2.1.3. Suppressed HBV DNA

The number of occurrences each participant has HBV DNA <LLOQ (overall and separately for HBV DNA detectable and HBV DNA TND) will be determined and summarized by intervention arm using frequency distributions and descriptive statistics. Additionally, the number of occurrences will be displayed graphically.

The same analyses will also be performed for HBV DNA < 60 IU/mL.

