## 5.1.3. Visit Windows

As participants do not always adhere to the protocol visit schedule, the following rules are applied to assign actual visits to analysis visits. All visits for all assessments (safety, efficacy or PK) will be uniquely allocated within each phase to an analysis time point based on the analysis relative day (ADY) compared with the target day based on Table 3. All assignments will be made in chronological order. Once a visit date is assigned to a visit window, it will no longer be used for a

later time point except for the end of study intervention period (EOSI) and end of study (EOS) visits. If a participant has 2 or more actual visits in 1 visit window, the visit closest to the target day will be used as the protocol visit for that visit window. The other additional visit(s) will not be used in the summaries or analyses, but they can be used for determination of clinically important endpoints. If 2 actual visits are equidistant from the target day within a visit window, the later visit is used. If there are two or more measurements on the same day, then the last measurement in chronological order will be used. If the time of the assessment is not available, the highest record/sequence number will be selected.

The listings and spaghetti plots will include all measurements, also those multiple assessments with the same visit window/phase.

End of study intervention (EOSI) and end of study (EOS) time points will be included in all analyses over time unless otherwise stated.

Table 3 provides the analysis time points and time intervals for each visit per analysis phase.

An alarsia mbaaa	Toward Dav	Analysis time point	Analysis time point	Time interval
Analysis phase	Target Day	(week)	(label)	(days)
Screening	-∞-	-1	Screening	<0
Study	1	0	Baseline	Pre-dose: 1
Intervention				
period				
	8	1	Week 1	[2, 11]
	15	2	Week 2	[12, 18]
	22	3	Week 3	[19, 25]
	29	4	Week 4	[26, 43]
	57	8	Week 8	[44, 71]
	85	12	Week 12	[72, 99]
	113	16	Week 16	[100, 127]
	141	20	Week 20	[128, 155]
	169	24	Week 24	[156, 183]
	Last visit in study	25ª	EOSI a	
	intervention period			
Follow-up	29	28	Follow-up Week 4	[1, 43]
	57	32	Follow-up Week 8	[44, 71]
	85	36	Follow-up Week 12	[72, 99]
	113	40	Follow-up Week 16	[100, 127]
	141	44	Follow-up Week 20	[128, 155]
	169	48	Follow-up Week 24	[156, 197]
	225	56	Follow-up Week 32	[198, 253]
	281	64	Follow-up Week 40	[254, 309]
	337	72	Follow-up Week 48	[310, +∞]

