#### 5.8.3.2. Interim Analyses

Interim analyses (IAs) may be conducted to assess safety and efficacy to support the sponsor's interactions with health authorities, as well as to inform decisions about additional studies and/or investigation of other treatment combinations. The optional IAs are planned when:

- All randomized participants have completed Week 24 or discontinued earlier.
- All randomized participants have completed FU Week 12 or discontinued earlier.

Depending on the enrollment rate, any of the above IAs may be skipped if it is too close to the predicted timing of any adjacent interim cut-offs and additional IAs may be performed by the sponsor to support interactions with health authorities.

The primary analysis will be conducted at the time when all participants have completed FU Week 24 or discontinued earlier.

Both primary and interim analyses will be based on all data available at the prespecified cut-off time points and may include data at later time points for those participants who have reached subsequent visits.

The final analysis will be conducted at the time when all participants have completed the last study visit (FU Week 48) or discontinued earlier.

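### The per-participant count of suppressed HBV DNA results has no denominator, so it mixes suppression with the number of visits assessed

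*SAP*

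**What the plan says.** SAP 5.4.2.1 gives the main analysis of every binary secondary endpoint: "The count and proportion (%) of participants achieving the endpoints defined in Section 5.4.1.1 will be summarized". Suppressed HBV DNA is among the endpoints that also receive a 90% CI, and LOCF "will be used for HBsAg seroclearance and Suppressed HBV DNA analyses at Week 24" and at FU Weeks 12, 24, 32 and 48. The section then introduces its subsections: "Subsections below describe the additional analyses planned for only those specific other secondary binary endpoints that require further evaluations".

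One of these is SAP 5.4.2.1.3. It takes "The number of occurrences each participant has HBV DNA <LLOQ", overall and separately for detectable and target-not-detected results. These counts "will be determined and summarized by intervention arm using frequency distributions and descriptive statistics", with a graph, and "The same analyses will also be performed for HBV DNA < 60 IU/mL". It does not mention the number of HBV DNA results each participant has.

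Three other rules bear on the count. SAP 5.4 and 5.4.2 analyse secondary endpoints on observed cases, and 5.4.2 presents summaries by arm and analysis phase unless otherwise specified. SAP 5.8.3.2 says that the primary and interim analyses "may include data at later time points for those participants who have reached subsequent visits". SAP 5.1.3 says: "End of study intervention (EOSI) and end of study (EOS) time points will be included in all analyses over time unless otherwise stated".

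**The concern.** A count of events is interpretable when everyone has the same number of opportunities. Here the opportunities are HBV DNA results, and they differ between participants through drop-out, missed samples and, at a data cut, date of enrolment. With observed-case data an absent result and a non-suppressed result both leave the count one lower, and the summary cannot tell them apart.

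The population makes this more than a formality. Entry requires HBV DNA <60 IU/mL on two measurements (Protocol 5.1, criterion A03) and NA treatment continues through follow-up (SAP 1.2). For <60 IU/mL, and plausibly for <LLOQ overall, most results should be suppressed, so differences in the count may come mainly from attendance. Two arms could then show different distributions in this table and figure with no difference in suppression.

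**Working it through.** The plan states no figure for this summary, so there is nothing to reproduce. The check uses the sampling schedule.

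**Inputs**
- Post-baseline HBV DNA samples in the intervention phase (Protocol 1.3.1): Weeks 2, 4, 8, 12, 16, 20, 24 = 7.
- Follow-up samples (Protocol 1.3.2): FU Weeks 4, 8, 12, 16, 20, 24, 32, 40, 48 = 9.
- Total: 7 + 9 = 16, the same in both arms.
- Attrition assumed in Protocol 9.2: about 10%. Arm 1 has 18 participants, and 2/18 = 11%.

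**Individual level, follow-up phase**
- Lost after FU Week 12, always suppressed: count 3; proportion 3/3 = 100%.
- Completer suppressed at 6 of 9 visits: count 6; proportion 6/9 = 67%.

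The count puts the less suppressed participant ahead. This reversal does not require near-universal suppression.

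**Arm level, everyone always suppressed**
- Whole-study count, 2 of 18 lost after Week 24: 16 − 9 × 2/18 = 15.0, against 16.0 in an arm with no losses.
- Same losses, by phase: 7.0 in both arms during the intervention. In follow-up the two have no observed results; if they drop out of the summary, both means are 9.0.
- Follow-up count, 2 of 18 lost after FU Week 12: 9 − 6 × 2/18 = 8.3, against 9.0.

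Presentation by phase removes the difference when loss coincides with a phase boundary, but not when it falls within a phase.

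**Data cut at FU Week 24**

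An always-suppressed participant has 6 follow-up results if FU Week 24 is the latest visit and up to 9 if later visits are included: 13 to 16 over the whole study. Enrolment date alone sets where in that range the participant falls.

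**Dependence on the suppression rate**

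A simulation of the whole-study count (16 visits, drop-out time uniform over visits, beta-binomial suppression with within-participant correlation 0.2 at 99% and 0.3 otherwise, 200,000 draws) gives the share of variance in the count explained by visits attended. The suppression rates and correlations are assumptions; the documents give neither.

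| Attrition | 99% suppressed | 95% | 90% | 70% | 50% |
|---|---|---|---|---|---|
| 5% | 87% | 48% | 30% | 10% | 5% |
| 10% | 92% | 64% | 46% | 18% | 9% |
| 20% | 96% | 78% | 62% | 30% | 15% |

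At 99% suppression, moving from no attrition to 10% lowers the mean count from 15.8 to 15.0, while the mean per-participant proportion stays at 0.99. With no attrition the count is exactly 16 times the proportion.

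**EOSI and EOS**

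These time points reuse the last visit of the intervention period and of the study, and SAP 5.1.3 exempts them from the rule that a visit is used once. If a programmer treats the count as an analysis over time, those results are counted twice. SAP 5.4.2.1.3 does not settle this.

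**The case against.** The strongest reply is that the endpoint already has a proper analysis. SAP 5.4.2.1 gives proportions of participants by time point with 90% CIs and LOCF at the key visits, and a reader of the study report would judge suppression from those. The count is expressly additional and descriptive: no test between arms is planned on it, a frequency distribution shows a few low scores for what they are, and SAP 5.2 tabulates discontinuation by arm. All of this stands, and it limits the point to one table and figure for each cut-off. It does not make that output interpretable, because LOCF applies to named time points and not to a count across visits.

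Second, a reader might infer that the count measures attendance and not suppression. The documents do not support that. Entry is at <60 IU/mL but the LLOQ is 20 IU/mL (SAP 5.1.9, Table 4), so a participant can enter above LLOQ. The split between detectable and target not detected can vary with full attendance. At suppression rates of 70% or below, the simulation attributes less than a third of the variance to visits.

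Third, imbalance between arms is not inevitable. Randomisation in permuted blocks should balance enrolment dates. Stopping JNJ-3989 early does not end sampling, since participants enter follow-up. At the final analysis every remaining participant has reached FU Week 48, so staggered enrolment no longer matters. Drop-out and missed samples remain.

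Fourth, a proportion has its own weakness: 1/1 and 16/16 both give 100%. That is a reason to show the number of assessments beside it.

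**Conclusion.** The point holds as a small improvement to a descriptive secondary summary. Without a denominator the count confounds suppression with the number of visits assessed, enough to reverse the order of two participants (3 against 6, when the proportions are 100% and 67%) and to separate two always-suppressed arms by 0.7 in follow-up (8.3 against 9.0) when 2 of 18 leave one arm after FU Week 12. That arm example assumes all losses fall in one arm at one time. The effect is largest for <60 IU/mL and plausibly for <LLOQ overall, weaker for any category with a lower rate, and nil with complete, equal follow-up.

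Two stronger readings should not be drawn. The endpoint as a whole is not left without a denominator, because the by-visit proportions supply one. Double counting through EOSI and EOS is a possibility left open by the wording, not something the SAP prescribes. The primary test, alpha and power are unaffected.

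**What to change.** In SAP 5.4.2.1.3, define the statistic by analysis phase as the participant's suppressed results divided by that participant's non-missing post-baseline HBV DNA results, taking one result per analysis visit and not counting EOSI or EOS again. Show the number of assessments alongside. Add the number of participants with any non-suppressed result. Apply this to <LLOQ overall, to the detectable and target-not-detected categories, and to <60 IU/mL.

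The cost is a sentence or two in the SAP and a changed table and figure for each cut-off; no new data are needed. The original count can stay beside the proportion as its numerator, so nothing planned is lost. SAP Amendment 2 already follows the primary analysis, so the change should be recorded as made after it; for a descriptive summary that is a matter of documentation only.

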## 5.4.2.1.4. Flares

The incidence rate will be calculated and summarized for on-treatment biochemical flares by intervention arm. Additionally, for each participant the total number of flares the participant experienced will be counted by type. Such counts will be used to summarize the distribution of the total number of flares by type and intervention arm.

The number and percentage of participants with ALT flares will be calculated by the peak ALT value during the flare using the following cut-offs:

- <3 x ULN
- $\geq$  3-<5 x ULN
- $\geq$  5-<10 x ULN
- $\geq 10 \text{ x ULN}.$

The incidence rate of flares will also be calculated before and after week 12.

For on-treatment biochemical flares, the incidence of flares causing treatment discontinuation will be summarized by intervention arm. Similarly, the incidence of flares followed by the achievement of HBsAg seroclearance (at any time) will be summarized by flare type and intervention arm.

Flares that are associated with signs of liver decompensation will be provided in a listing.

# 5.4.2.2. Continuous Endpoints

# 5.4.2.2.1. HBsAg, HBeAg, HBV DNA and ALT

Descriptive statistics on actual values (original unit and/or log10 transformed values) over time in HBsAg, HBeAg, HBV DNA, and ALT (original unit) will be summarized by intervention arm. Changes from baseline (log10 transformed values) over time in HBsAg, HBeAg, and ALT (original unit) and changes from RTs (log10 transformed) over time in HBsAg will be summarized by intervention arm. Mean (+/- SE) plots of the actual values in HBsAg, HBV DNA and ALT (original unit) and change from baseline (log10 transformed)) will be presented over time in HBsAg and ALT (original unit) - by intervention arm and analysis phase. Change from RTs (log10 transformed) will be presented over time in HBsAg will be summarized by intervention arm and analysis phase. Change from RTs (log10 transformed) will be presented over time in HBsAg will be summarized by intervention arm and analysis phase. Change from RTs (log10 transformed) will be presented over time in HBsAg will be presented over time in HBsAg by intervention arm and analysis phase. The change from baseline value to the nadirs (i.e. maximum decrease for each participant) in HBsAg will be summarized descriptively by intervention arm. Box plots of the changes to nadirs in HBsAg will display the distribution by intervention arm.

Change from baseline based on  $log_{10}$  transform for quantitative HBsAg, HBeAg and HBV DNA will be analyzed using mixed effects model for repeated measures [MMRM]) including intervention arm, analysis time point (week), and the randomization stratification factor (ie, absolute HBsAg value at screening [<100 IU/mL, 100 to <1,000 IU/mL versus  $\geq$ 1,000 IU/mL]) as fixed effects. In addition, the above model will be augmented with an intervention arm-by-analysis week interaction term (i.e. treatment-by-time interaction term) to evaluate the change of treatment effect over time. The covariance structure will include a random intercept at the level of the participant to capture between-participant variability, while within-participant variability will be captured with an unstructured (type=UN) covariance matrix. In case of convergence problems, simpler variance-covariance structures such as Toeplitz or AR (1) will be considered. The selection of any of these structures will be determined after exploration of the observed correlation structure. The LS mean of change from baseline, standard error (SE), 90% confidence interval (CI) and p-values will be provided.

Descriptive statistics on actual values (original unit and  $log_{10}$  transformed values) in HBsAg, HBeAg and HBV DNA and changes from baseline ( $log_{10}$  transformed values) at end of treatment

in HBsAg, HBeAg and will be summarized by study intervention arm by outcome response (i.e. by HBsAg seroclearance at FU Week 24 and FU Week 48).

Waterfall plots for actual values, changes from baseline of HBsAg will also be presented.

Descriptive statistics of the absolute values, changes from baseline over time in ALT will be summarized by intervention arm and analysis phase for those participants who had ALT elevation at baseline. An additional summary of descriptive statistics of the ALT absolute values and changes from baseline over time will be summarized by intervention arm and analysis phase for those participants who had ALT values within the normal range at baseline.

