	Last visit in the	999 b	EOS b	
	study			

Table 3:Visit Windows

a End of study intervention (EOSI) visit will be the last post-baseline visit in study intervention period.

b End of study (EOS) visit (last available data during the follow-up visit) will be the last visit in the study.

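### The SAP fits two repeated-measures models of HBsAg change but names no model, week or contrast for the arm comparison; an arm effect pooled over all visits would understate a late difference

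*SAP*

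**What the plan says.** SAP 5.4.2.2.1 specifies an MMRM of change from baseline in log10 HBsAg (also HBeAg and HBV DNA), "including intervention arm, analysis time point (week), and the randomization stratification factor", all as fixed effects. This model has one arm effect across visits. The SAP then says that "the above model will be augmented with an intervention arm-by-analysis week interaction term", to see how the treatment effect changes over time. For output it says only: "The LS mean of change from baseline, standard error (SE), 90% confidence interval (CI) and p-values will be provided".

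On covariance, the model has a "random intercept at the level of the participant to capture between-participant variability" together with an unstructured (UN) within-participant matrix. If convergence fails, "simpler variance-covariance structures such as Toeplitz or AR (1) will be considered". The SAP adds: "The selection of any of these structures will be determined after exploration of the observed correlation structure".

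Three other places matter:

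- SAP 5.1.3: "End of study intervention (EOSI) and end of study (EOS) time points will be included in all analyses over time unless otherwise stated". A footnote to its Table 3 adds: "End of study intervention (EOSI) visit will be the last post-baseline visit in study intervention period".
- SAP 5.4.2: arm comparisons of secondary endpoints are optional and unadjusted for multiplicity. Summaries and graphs are given by arm and analysis phase by default.
- Protocol 4.1 and 1.3.1 (footnote b): Arm 1 has nivolumab at Week 16, Arm 2 at Weeks 16, 20 and 24, and blood is drawn before dosing unless indicated otherwise.

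**The concern.** The two models answer different questions. The arm-by-week model gives a contrast at each visit. The model without interaction gives a single weighted average over visits, and many of those visits come before the arms can differ. The SAP does not say which one will be shown as the difference between one and three infusions, at which week, or whether the p-value refers to arm, to arm at a week, or to the interaction. For seroclearance the same SAP does name weeks and a direction, Arm 1 minus Arm 2 (5.4.2.1).

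At stake is the main continuous comparison of the two regimens. If the pooled arm effect were presented as that comparison, a real late difference would look smaller than it is. With nothing named, the choice could also be made after the results are known.

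**Working it through.** The plan gives no figure for this model, so there is none to reproduce.

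**Step 1: visits.** The quantitative HBsAg rows in Protocol 1.3.1 and 1.3.2 give:

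- On treatment, post-baseline: Weeks 1, 2, 3, 4, 8, 12, 16, 20, 24 = 9.
- Follow-up: FU Weeks 8, 12, 16, 20, 24, 32, 40, 48 = 8 (none at FU Week 4).

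The first infusion that differs is at Week 20, after that visit's sample. So 8 of 17 samples (Weeks 1 to 20) cannot differ by arm as assigned, and 9 can (Week 24 and all of follow-up).

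**Step 2: share of a later difference kept.** With complete data, the no-interaction arm effect weights visits by w = V⁻¹1 / (1ᵀV⁻¹1), where V is the visit covariance. For a difference of 0 up to Week 20 and constant from Week 24, the share kept is wᵀd, with d = 0 for the first 8 visits and 1 for the last 9. Equal weights give 9/17 = 53%. The documents give no variances or correlations for this trial, so these are assumed:

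| Correlation | Constant variance | UN weights, SD rising 0.3 to 0.5 |
|---|---|---|
| Compound symmetry, 0.3-0.95 | 53% | zero or negative |
| AR(1) by visit order, 0.3-0.95 | 51-53% | 13-39% |
| Spatial power, 0.80-0.99 per week | 55-66% | 8-52% |

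The 8% is at 0.99 per week; over 0.80-0.95 the range is 42-52%. Rising variance lowers the share because the weight moves to the early, less variable visits. A constant-variance AR(1) fit still keeps 51-53% even if the true SD rises, because its weights ignore the rise. With data only to FU Week 24, 6 of 14 visits can differ and the constant-variance share is 43-54%.

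**Step 3: is rising variance plausible?** Protocol 2.1 cites HBsAg change after nivolumab 0.3 mg/kg (n = 12). SD = half-width × √12 / t, with t = 2.201 on 11 df:

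- Week 12, CI -0.46 to -0.14: 0.16 × 3.464 / 2.201 = 0.25.
- Week 24, CI -0.83 to -0.13: 0.35 × 3.464 / 2.201 = 0.55.

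The group is small and the regimen differs, but the direction is towards rising variance.

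**Step 4: what dilution does to inference.** Assume a later difference of 0.5 log10, constant SD 0.5, and 18 vs 19 participants. For compound symmetry 0.7:

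- One visit: SE = 0.5 × √(1/18 + 1/19) = 0.164; z = 3.04.
- Pooled: SE = 0.164 × √((1 + 16 × 0.7)/17) = 0.139; z = 0.5 × 0.529 / 0.139 = 1.90.
- Nine visits after Week 20: SE = 0.164 × √((1 + 8 × 0.7)/9) = 0.141; z = 3.55.

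Over all the constant-variance structures in the table, pooled z is 1.65-5.64 and restricted z is 3.11-7.15. Within a structure the pooled z is 21-47% lower. Against a single-visit contrast it can be lower or higher.

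The pooled nominal 90% CI covers the later difference with probability Φ(1.645 - b) - Φ(-1.645 - b), where b = difference × (1 - share) / SE. For the case above, b = 0.5 × 0.471 / 0.139 = 1.69 and coverage is 48%. Across structures it is 0-57% for a difference of 0.5, 28-81% for 0.25 and 77-89% for 0.10.

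A simulation (4,000 runs, true later difference 0.50) gave pooled means of 0.256-0.268 and FU Week 24 contrasts of 0.498-0.505.

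**Step 5: if fitted by phase.** In the study-intervention phase 8 of 9 visits cannot differ. Under constant variance the share is 11% (compound symmetry), 14-43% (AR(1)) or 21-46% (spatial power). In follow-up it is 100%. The SAP does not say whether the MMRM spans both phases.

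**Step 6: covariance specification.**

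- UN on 17 visits has 17 × 18 / 2 = 153 parameters, for 37 participants. A random intercept adds one constant to every entry, which UN already absorbs: 154 parameters, rank 153.
- Read literally, 5.1.3 adds EOSI and EOS to the model. For completers these copy Week 24 and FU Week 48: 19 time points of rank 17, so UN is singular.
- Standard Toeplitz and AR(1) assume constant variance and equal spacing; the visits are 1, 4 or 8 weeks apart.

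**The case against.** The strongest reply is that the SAP already plans the undiluted analysis. The arm-by-week model is there expressly to follow the treatment effect over time, and changes in HBsAg from the reference timepoints are summarised by arm. Arm comparisons of secondary endpoints are optional and the primary test is untouched. All of that stands, and it limits the point to which result is reported.

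A second reply is that a no-interaction effect estimates an average over visits, so a CI that misses the late difference reflects another estimand, not an error. That also stands. The coverage figures matter only if the average is read as the late difference, and the lowest come from an assumed 0.5 log10, larger than the whole mean decline in the cited nivolumab group (-0.48 at Week 24). At 0.10 log10 coverage is near nominal in most structures.

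Third, the random intercept and the EOSI/EOS time points are matters of implementation. The redundant intercept leaves the marginal covariance unchanged, and one sentence settles EOSI and EOS. Both still need correcting, because the model as written cannot be fitted as stated.

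A reader might infer that the SAP will report the pooled effect as the arm difference, or that half to two-thirds of a late difference is what the plan recovers. The documents support neither: no model is named, and that share needs constant variance, which the first-choice UN does not assume.

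**Conclusion.** The point holds as a gap in one secondary analysis. The SAP does not name the model, week or contrast for its reported arm comparison, and one of its two models gives a diluted answer if pooled over all visits. The dilution leaves about 51-66% of a constant later difference under constant variance. Under UN with the SD rising from 0.3 to 0.5 it leaves about 8-52% with AR(1) or spatial-power correlation, and zero or less with compound symmetry.

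These sizes rest on assumed variances and correlations, complete data, and a later difference that is constant from Week 24. The real contrast may be smaller: the SAP version history records a halt of nivolumab dosing on 20 June 2023, and the documents do not say how many infusions were missed. The count of 8 in 17 samples, the missing specification and the redundant random intercept need no such assumptions.

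**What to change.** In SAP 5.4.2.2.1:

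- Take the arm comparison from the arm-by-week model, fitted across both phases. Report Arm 1 minus Arm 2 with 90% CI at FU Week 24, to match the primary endpoint, with Week 24 and FU Week 48 as supporting.
- Do not report the no-interaction effect pooled over all visits as the arm difference. Drop that model, or restrict it to the 9 visits after Week 20.
- Delete the random intercept, and state that EOSI and EOS are not model time points.
- Add Day 1 log10 HBsAg as a covariate. The gain in precision is small, and leaving it out causes no bias.
- Fix the order of fallback covariance structures in advance, using structures that allow unequal variances and unequal spacing, for example heterogeneous Toeplitz and then spatial power on actual weeks with unequal variances. Name the degrees-of-freedom method, for example Kenward-Roger.

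The cost is SAP wording and the reprogramming of one secondary model. No new data are needed.
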